2.3.3.4. Cardiac Endpoints

The following endpoints will be evaluated in the Cardiac Evaluable Population (see Section 5).

For these subjects, cardiac response, as assessed by N-terminal pro-brain natriuretic peptide (NT-proBNP), categories are defined as (modified from Table 2 in [Comenzo, 2012](#)):

Response	Stable Disease	Progression
Decrease in NT-proBNP from baseline of >30% and >300 ng/L or decrease in NYHA class of ≥ 2 in subjects with baseline NYHA class III or IV	Assessment was neither Response nor Progression	Increase in NT-proBNP from baseline of >30% and >300 ng/L

Best response is defined as the most favorable category (response, stable, or progression) across all visits. Subjects will be classified as responders or non-responders. Non-response is defined as either stable or progression.

- Cardiac response from NEOD001 and OLE baselines (see Section 2.2.4), as assessed by NT-proBNP response criteria, at each visit
- Cardiac best response from NEOD001 and OLE baselines (see Section 2.2.4), as assessed by NT-proBNP response criteria. Best response will be over the course of the study.
- Change and percent change from NEOD001 and OLE baselines (see Section 2.2.4) to each visit in NT-proBNP

2.3.3.5. Renal Endpoints

The following endpoints will be evaluated in the Renal Evaluable Population (see Section 5).

For these subjects, renal response categories (modified from [Palladini, 2014](#)) are defined as:

Response	Stable	Progression
$\geq 30\%$ decrease from baseline or $< 0.5\text{g}/24$ hours post-baseline result of proteinuria (measured by 24-hour urine total protein excretion) in the absence of renal progression	Assessment was neither Response nor Progression	$\geq 25\%$ decrease in eGFR from baseline Note: if assessment qualifies as both Response and Progression, then assessments will be counted as progression

Best response is defined as the most favorable category (response, stable, or progression) across all visits. Subjects will be classified as responders or non-responders. Non-response is defined as either stable or progression.

- Renal response from NEOD001 and OLE baselines (see Section 2.2.4) at each visit
- Renal best response from NEOD001 and OLE baselines (see Section 2.2.4). Best response will be evaluated over the course of the study.
- Change and percent change from NEOD001 and OLE baselines (see Section 2.2.4) to each visit in creatinine, proteinuria, and estimated glomerular filtration rate (eGFR)
- Time to eGFR ≤ 15 mL/min/1.73 m² (Chronic Kidney Stage 5) from NEOD001 and OLE baselines (see Section 2.2.4)

2.3.3.6. Peripheral Neuropathy Endpoints

The following endpoints will be evaluated in the Peripheral Neuropathy Evaluable Population (see Section 5). Peripheral neuropathy response and progression as defined in Coelho, 2012, are those with an increase from baseline in Neuropathy Impairment Score in the Lower Limbs (NIS-LL) total score of <2 points and those with an increase from baseline in NIS-LL of ≥ 2 points, respectively.

- Change and percent change from NEOD001 and OLE baselines (see Section 2.2.4) to each visit in the NIS-LL total score to each visit
- Peripheral neuropathy response from NEOD001 and OLE baselines (see Section 2.2.4) at each visit
- Change and percent change from NEOD001 and OLE baselines (see Section 2.2.4) in the 3 NIS-LL component scores (sensory function, reflexes, muscle strength) to each visit

3. SAMPLE SIZE JUSTIFICATION

Not applicable as this is an extension study for subjects previously enrolled and treated for at least 9 months in Study NEOD001-001.

4. GENERAL STATISTICAL METHODS

4.1. Reporting Conventions

Individual subject data obtained from electronic case report forms (eCRFs), central laboratories, external sources, and any derived data will be presented in data listings by subject. The primary data source will be used for all analyses. All data listings that contain an evaluation date will contain a relative study day. Pre-treatment and on-treatment study days are numbered relative to the day of the first dose of study drug in the OLE which is designated as Day 1. The preceding day is Day -1, the day before that is Day -2, etc.

All output will be incorporated into Microsoft Word rich text format (.rtf) files, sorted and labeled according to the International Council for Harmonisation (ICH) recommendations, and formatted to the appropriate page size(s).

For categorical variables, summary tabulations of the number and percentage of subjects within each category (with a category for missing data) of the parameter will be presented. Percentage calculations will be based on non-missing data, unless otherwise specified. Percentages are rounded to 1 decimal place, unless otherwise specified.

For frequency counts of categorical variables, categories whose counts are zero will be displayed for the sake of completeness. For example, if none of the subjects discontinued due to “lost to follow-up,” this reason will be included in the table with a count of 0. Percentages based on frequency counts will be presented to one decimal place, and values less than 1% will be presented as “<1%.” Values less than 100% but greater than 99% will be presented as “>99%.”

For continuous variables, the number of subjects, mean, standard deviation (SD), median, 25th quartile (Q1), 75th quartile (Q3), minimum, and maximum values will be presented. The precision of summary statistics, unless otherwise specified will be as follows: mean and median to 1 more decimal place than the raw data, and SD to 2 decimal places more than the raw data. In general, the number of decimal places should not exceed 3 decimal places unless appropriate. Confidence intervals (CIs) will be provided and will be rounded to 1 decimal place, unless otherwise specified, in the table and listing shell.

For tables where rounding is required, rounding will be done to the nearest round-off unit. For example, when rounding to the nearest integer, values $\geq XX.5$ will be rounded up to $XX+1$ (e.g., 97.5 will round up to 98), while values $<XX.5$ will be rounded down to XX (e.g., 97.4 will round down to 97).

4.2. Computing Environment

All descriptive statistical analyses will be performed using SAS statistical software Version 9.4 or higher, unless otherwise noted. Medical history and AEs will be coded using Medical Dictionary for Regulatory Activities (MedDRA) version 19.0. Concomitant medications will be coded using World Health Organization (WHO) Drug Dictionary, B2 Enhanced September 2015.

4.3. Partial Dates and Unknown Times

If only a partial date is available and is required for calculation, the following standards will be applied:

- Death Date
 - The last date that each subject was known to be alive will be identified as the greatest date associated with the subject’s completed assessments, including telephone contacts at which the subject was confirmed to be alive.
 - For missing day only – Day will be imputed as the first day of the month (i.e., 1) with the following exception: if the partial date falls in the same month as the last known alive date, then the partial date will be imputed to equal the last known alive date.
 - For missing day and month – Day and month will be imputed as the first day of the year (i.e., 1 January) with the following exception: if the partial date falls in the same year as the last known alive date, then the partial date will be imputed to equal the last known alive date.
- Start Dates (e.g., event date, AE onset date, start date of medication, or hospitalization admission date)
 - For missing start day only – Day will be imputed as the first day of the month (i.e., 1) with the following exception: if the partial date falls in the same month and year as the date being used in the calculation (e.g., first infusion date, informed consent date), then the partial date will be imputed to equal the date being used for the calculation.
 - For missing start day and month – Day and month will be imputed as the first day of the year (i.e., 1 January) with the following exception: if the partial date falls in the same year as the date being used in the calculation (e.g., first infusion date, informed consent date), then the partial date will be imputed to equal the date being used for the calculation.
 - When applicable, imputed start dates must be prior to the stop date.
- Stop Dates (e.g., AE resolution date or stop date of medication)
 - For missing stop day only – Day will be imputed as the last day of the month (i.e., 28, 29, 30, or 31).
 - For missing stop day and month – Day and month will be imputed as the last day of the year (i.e., 31 December).
 - Imputed stop dates must be on or after the start date.

If a time required for calculation related to exposure is missing, the following standards will be applied:

- If start time is missing for an infusion where the volume recorded on the eCRF is greater than 0 mL then start time will be imputed as the pre-dose time of vital signs at the same

visit + 1 minute. This should only be done for the first dose time within a given visit should there be more than one record.

- If stop time is missing for an infusion where the volume is greater than 0 mL then stop time will be imputed as the ‘immediately after infusion’ time of the vital signs at the same visit - 1 minute. This will only be done for the last dose time within a given visit should there be more than one record.
- If vital sign assessment times are not available, infusion start date/time is missing, and infusion stop date/time is non-missing then the start date/time will be imputed as stop date/time - 2 hours at the Month 1 Day 1 visit or as the stop date/time - 1 hour for all other visits.
- If vital sign assessment times are not available, infusion stop date/time is missing, and infusion start date/time is non-missing then the stop date/time will be imputed as start date/time + 2 hours at the Month 1 Day 1 visit or as the start date/time + 1 hour for all other visits.

All data recorded on the case report form will be included in data listings that will accompany the CSR.

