1.3.2 Clinical Safety

The safety and tolerability of NEOD001 have been investigated in the Phase 1/2 study (Study NEOD001-001) in the US, and are being investigated in the following ongoing global studies:

- Phase 1/2 open-label extension study (Study NEOD001-OLE001)
- Phase 2b study (Study NEOD001-201)
- Phase 3 study (Study NEOD001-CL002)

Study NEOD001-001 was a Phase 1/2 open-label, dose escalation study of the IV administration of single-agent NEOD001 in subjects with AL amyloidosis, which enrolled 27 subjects in the Escalation Phase in 7 cohorts (evaluating dose levels from 0.5 mg/kg to 24.0 mg/kg) and enrolled an additional 42 subjects in the Expansion Phase. The most frequently reported treatment-emergent adverse events (TEAEs) overall in Study NEOD001-001 (occurring in $\geq 10\%$ of subjects [N=69], regardless of relationship to NEOD001) were fatigue, nausea, upper respiratory tract infection, diarrhea, anemia, blood creatinine increased, dizziness, constipation, cough, headache, edema peripheral, vomiting, pain in extremity, back pain, dyspnea, edema, muscle spasms, rash, and urinary tract infection (Gertz et al, 2016). No confirmed anti-NEOD001 antibodies were detected. No dose-limiting toxicities (DLTs) or related serious adverse events (SAEs) were reported.

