9.2.9. Other Adverse Events: Infusion Reactions

The crude incidence of infusion associated TEAEs by MedDRA SOC and PT will be summarized. This is a subset of the AEs where the question “Was the event an infusion-associated adverse event?” is checked “Yes”. In addition, the cumulative incidences of TEAEs will be summarized.

If applicable, the crude incidence anaphylactic reaction, defined as the broad algorithmic standardized MedDRA query (SMQ) of “Anaphylactic reaction”, defined in [Appendix 5](#), will be summarized.

In order to explore the temporal relationship of TEAEs that may be associated with the infusion, the crude incidence of all TEAE occurring within 1 day (AE start date – infusion date + 1 = 1) of an infusion will be summarized.

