APPENDIX 5. ANAPHYLACTIC REACTION SMQ

An Adverse Event or group of Adverse Events occurring on the same day should be flagged as Anaphylactic Reaction per SMQ if the AE(s) meets one or more of the following criteria:

- Any term from group A
- Any two terms, with one from group B and one from group C
- Any two terms, with one from group D and one from either group B or group C

Group A Terms	
Preferred Term	Preferred Term Code
Anaphylactic reaction	10002198
Anaphylactic shock	10002199
Anaphylactic transfusion reaction	10067113
Anaphylactoid reaction	10002216
Anaphylactoid shock	10063119
Circulatory collapse	10009192
Dialysis membrane reaction	10076665
Kounis syndrome	10069167
Shock	10040560
Shock symptom	10040581
Type I hypersensitivity	10045240

Group B Terms	
Preferred Term	Preferred Term Code
Acute respiratory failure	10001053
Asthma	10003553
Bronchial oedema	10056695
Bronchospasm	10006482
Cardio-respiratory distress	10049874
Chest discomfort	10008469
Choking	10008589
Choking sensation	10008590

Group B Terms	
Preferred Term	Preferred Term Code
Circumoral oedema	10052250
Cough	10011224
Cyanosis	10011703
Dyspnoea	10013968
Hyperventilation	10020910
Irregular breathing	10076213
Laryngeal dyspnoea	10052390
Laryngeal oedema	10023845
Laryngospasm	10023891
Laryngotracheal oedema	10023893
Mouth swelling	10075203
Nasal obstruction	10028748
Oedema mouth	10030110
Oropharyngeal oedema	10078783
Oropharyngeal spasm	10031111
Oropharyngeal swelling	10031118
Pharyngeal oedema	10034829
Respiratory arrest	10038669
Respiratory distress	10038687
Respiratory failure	10038695
Reversible airways obstruction	10062109
Sensation of foreign body	10061549
Sneezing	10041232
Stridor	10042241
Swollen tongue	10042727
Tachypnoea	10043089
Throat tightness	10043528
Tongue oedema	10043967
Tracheal obstruction	10044291

Group B Terms	
Preferred Term	Preferred Term Code
Tracheal oedema	10044296
Upper airway obstruction	10067775
Wheezing	10047924

Group C Terms	
Preferred Term	Preferred Term Code
Allergic oedema	10060934
Angioedema	10002424
Erythema	10015150
Eye oedema	10052139
Eye pruritus	10052140
Eye swelling	10015967
Eyelid oedema	10015993
Face oedema	10016029
Flushing	10016825
Generalised erythema	10051576
Injection site urticaria	10022107
Lip oedema	10024558
Lip swelling	10024570
Nodular rash	10075807
Ocular hyperaemia	10030041
Oedema	10030095
Periorbital oedema	10034545
Pruritus	10037087
Pruritus allergic	10063438
Pruritus generalised	10052576
Rash	10037844
Rash erythematous	10037855

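### Imputed AE onset dates can enter the infusion-day outputs and the same-day anaphylaxis query, because the SAP does not exclude them there

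*SAP*

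**What the plan says.** SAP 4.3 opens its rules with "If only a partial date is available and is required for calculation, the following standards will be applied". The rules for start dates name AE onset explicitly: "Start Dates (e.g., event date, AE onset date, start date of medication, or hospitalization admission date". A missing day becomes the 1st of the month, and a missing day and month become 1 January. The exception applies "if the partial date falls in the same month and year as the date being used in the calculation" (or the same year, when the month is missing too). The SAP illustrates that date only by example: "e.g., first infusion date, informed consent date), then the partial date will be imputed to equal the date being used for the calculation". One guard follows: where applicable, an imputed start must come before the stop date.

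Three outputs then depend on the exact day of onset:

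- SAP 9.2.9 has a summary introduced with "In order to explore the temporal relationship of TEAEs that may be associated with the infusion". It counts a treatment-emergent AE (TEAE) when start date minus infusion date plus 1 equals 1, that is, a difference of 0 days.
- SAP 9.2 has a listing of AEs whose onset falls on the date of any infusion.
- SAP Appendix 5 says "An Adverse Event or group of Adverse Events occurring on the same day should be flagged as Anaphylactic Reaction per SMQ" if it meets the criteria. Apart from single group A terms, these need two terms: B with C, or D with B or C.

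The only partial-date rule in the AE section (SAP 9.2) concerns treatment-emergent status. None of the three outputs excludes or flags imputed dates.

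**The concern.** A convention made to place an event before or after a milestone is being carried into outputs that test for coincidence on one day. Events of one subject that lack a day are all moved to the same date, so a coincidence can come from the rule and not from the data. Depending on how the reference date is read, an event that lacks a day can also be moved onto an infusion.

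The terms involved are common ones. Cough and dyspnoea are in group B; oedema and rash are in group C. All four are among the TEAEs reported in at least 10% of the 69 parent-study subjects (Protocol 1.3.2, a list that ends "pain in extremity, back pain, dyspnea, edema, muscle spasms, rash, and urinary tract infection").

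Safety is the primary objective and the study is small. With about 70 subjects, one such flag adds 1/70 = 1.4 percentage points to a crude incidence.

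**Working it through.** The plan gives no figure to reproduce here. The check applies the 4.3 rules to the three outputs.

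**Inputs.** Infusions every 28 (±5) days, Months 1 to 36 (Protocol 6.1.2); the 4.3 rules; the 9.2.9 formula; the Appendix 5 same-day rule. Assumption: AE onset is uniform from first dose to 30 days after last dose. The frequency of partial onset dates is not in the documents.

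**Two readings of the reference date.** The *first-infusion reading* takes the SAP's own example. The *any-infusion reading* takes the infusion date that the 9.2.9 formula uses. The wording permits both.

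**Chance benchmark.** At exact 28-day spacing, follow-up is 35 × 28 + 30 + 1 = 1,011 days with 36 infusion days, so 36/1,011 = 3.6% of true onsets fall on an infusion day. Two independent AEs in one month share a day with probability 1/31 to 1/28, or 3.2–3.6%.

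**Infusion-day outputs.** 20,000 simulated subjects, with spacing of exactly 28 days and then with ±5 days' jitter, stop-date guard not applied:

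| Share landing on an infusion day | Exact 28 days | With jitter |
|---|---|---|
| True onset | 3.5% | 3.4% |
| Day missing, any-infusion reading | 98.5% | 95.3% |
| Day missing, first-infusion reading | 4.9% | 5.1% |
| Day and month missing, any-infusion reading | 99.9% | 99.8% |
| Day and month missing, first-infusion reading | 21.2% | 20.7% |

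The 4.9% breaks down as follows. About 1.46% of AEs fall in the month of the first infusion and move to Day 1. The other 98.54% go to the 1st of their month, which is an infusion day 3.47% of the time: 1.46% + 98.54% × 3.47% = 4.9%. Outside the first-infusion month, this reading therefore gives chance level. Inside that month, both readings put the AE on an infusion day.

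**Same-day pairing.** Take two day-missing AEs of one subject in the same month.

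- First-infusion reading: both go to Day 1 if it is that month, otherwise both go to the 1st. They match, subject to the guard.
- Any-infusion reading: both go to that month's infusion date if there is only one. At 28-day spacing there are 365.25/28 = 13.04 infusions a year over 12 months, so about one month a year holds two, and the SAP does not say which applies.

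A day-missing AE can also be matched to a fully dated AE that happens to lie on the imputed date.

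**Example.** Infusion 10 March; cough (B) truly begins 14 March and rash (C) 27 March; both are recorded as March only. By true dates the 9.2.9 values are 14 − 10 + 1 = 5 and 27 − 10 + 1 = 18. Neither is an infusion-day event, and they are 13 days apart. With 10 March as reference, both are set to 10 March: each gives 10 − 10 + 1 = 1, and together they meet B+C. If the first infusion was in another month, both are set to 1 March: neither is an infusion-day event, but they still meet B+C, because Appendix 5 does not require closeness to an infusion.

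**The stop-date guard.** It blocks an imputed date only when the AE had ended on or before it. An event that starts in a month cannot end before the 1st, so the guard hardly touches the default rule. It can block a move to a later reference date, and can separate a pair that way. In the example it blocks nothing.

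**The case against.** The best case against acting has five parts.

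- **The named reference date is the first infusion.** On that reading the infusion-day effect is about 5%, near chance. This stands. A reader might infer that the rule turns every partial-date AE into an infusion-day event. The documents do not support that: it needs the any-infusion reading, and even then the figure for day-missing AEs is 95–98% before the guard.
- **These are not the only infusion-reaction outputs.** SAP 9.2.9 begins with infusion-associated TEAEs taken from the investigator's eCRF answer, which also feeds a listing in 9.2 and a row in 9.2.2. That answer needs no onset date for selection. This stands, and it limits the harm.
- **Partial dates may be rare.** Protocol 7.1 asks for full documentation of every AE, including onset date. Visits are monthly, and subjects are observed after each infusion, so true infusion-day reactions are the least likely to lack a day. This stands as far as it goes. The documents give no rate, and AEs elicited by a general question 28 days later may lack one.
- **The outputs are descriptive, and the query is deliberately broad.** True, but its breadth concerns which terms count, not whether their dates were observed. A separate review listing keeps the sensitivity.
- **Listings show the recorded data.** A careful reader could trace a flagged case back to a partial date. The summary tables would not show that anything needed tracing.

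**Conclusion.** The point holds in a limited form, as a specification gap that should be closed. The pairing problem exists under either reading: two day-missing AEs of one subject in the same month will usually share a date, against about 3% by chance. The conditions are the stop-date guard and, if any infusion is the reference, a single infusion in that month. Group A terms need no pair and are unaffected.

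The size of the infusion-day problem depends on a choice the SAP leaves open. For day-missing AEs it is about 95–98% under the any-infusion reading and about 5% under the first-infusion reading, against about 3.5% by true onset. With the month also missing, the first-infusion figure is about 21%. Two programmers could produce different tables from the same text.

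These percentages assume uniform onset and apply only to AEs with partial dates, whose number is unknown. A reader might go further and infer that the plan will create false anaphylaxis cases. The documents do not show that: any such flag is unverified, since the two events might have coincided, and there may be few or none.

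**What to change.** Leave SAP 4.3 in place for treatment-emergent status and for the life-table cumulative incidence in 9.2.1.2, which needs an onset time to assign each AE to an interval. Restricting 4.3 to treatment-emergent status alone would break that analysis and would remove imputation from the medication and hospitalization start dates that 4.3 also covers.

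Make the change where exact days matter:

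- In 9.2.9 and the matching 9.2 listing, count infusion-day AEs from complete, observed onset dates only.
- In Appendix 5, apply same-day pairing to complete, observed onset dates only.
- List partial-date AEs, including terms in the anaphylaxis query, separately for medical review.

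Alternatively, flag imputed dates and show these results with and without them; the reference date for 9.2.9 must then be stated. Using observed dates here also fits Protocol 8.7, which excludes imputation of missing data.

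The cost is a few sentences in the SAP and one listing, with no new data. The small downside is that a real reaction with an incomplete date appears in the review listing and not in the main count.

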5.4.3 Dose Reductions

Dose reductions may be allowed in the event that observed AEs are believed to be related to study drug, and which in consultation between the Investigator and the Medical Monitor, may be managed by a 50% reduction in dose. The duration of the dose reduction will be at the Investigator's discretion.

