- Other Assessments (Laboratory Manual) – every 3 months
 - Serum NEOD001 concentration
 - Serum anti-NEOD001 antibodies

- Additional samples for anti-NEOD001 antibodies and serum NEOD001 should be collected if a significant toxicity is observed

NEOD001 Administration:

Note: Subjects who present with symptomatic orthostatic hypotension or systolic BP <85 mmHg will have the study drug held

- Month 1-Day 1:
 - Administer NEOD001 IV using the infusion duration established during Study NEOD001-001 or over 60 (± 10) minutes (Section 5.3)
 - Assess vital signs including HR, BP, RR, and body temperature, halfway through the infusion (Section 6.3.2)
- All Other Months:
 - If the Month 1-Day 1 infusion was well tolerated without infusion-associated AEs, administer NEOD001 IV using the infusion duration established during Study NEOD001-001 or over 60 (± 10) minutes. If needed, see Section 5.4 for dose adjustment instructions.

After Infusion:

- Monitor subjects for 90 (± 10) minutes following completion of the study drug infusion. Beginning with the third infusion, the Investigator may decrease the postdose monitoring time to no less than 60 minutes, if no infusion-related reactions were observed in the previous infusions and allowed per the IRB/IEC (per Section 5.3). The Investigator may increase the monitoring time if deemed appropriate or per local standards. In the event of any clinical concerns or suspicious signs or symptoms after the infusion, the subject will remain under observation for as long as the Investigator deems it appropriate.
- Routine medications should not be administered in the 15 minutes after the completion of the NEOD001 infusion
- Vital signs including HR, BP, RR, and body temperature (Section 6.3.2):
 - Month 1-Day 1:
 - Immediately at end of infusion (EOI) (+5 minutes)
 - 30 (± 5) minutes after EOI
 - 60 (± 10) minutes after EOI
 - All Other Months:
 - Immediately at EOI (+5 minutes)

- 60 (\pm 10) minutes after EOI
- 12-lead ECG in triplicate (perform locally)
 - Within 15 minutes after EOI
- Serum NEOD001 concentration – every 3 months
 - EOI (record the time, but the sample can be collected at any time after the infusion on Day 1)

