9.1. Extent of Exposure

Study drug exposure during the OLE and separately for the original parent study (NEOD001-001) and OLE combined will be summarized including:

- Total Number of Infusions received will be determined for each subject by number of times the start time of drug infused is reported. If multiple infusion start times are reported on a single day, then only 1 infusion will be counted for that day. If the start time of drug infused is missing but total volume infused is greater than 0 mL, 1 infusion will be counted for that day.
- Total Number of Dose Interruptions will be determined for each subject by the number of times the IV was not completed in OLE, or segment outcome of the infusion was interrupted in parent study.
- Dose Strength (mg/kg) will be calculated for each subject at each OLE visit and each visit in parent study separately as follows:
 - For each OLE visit, dose (mg) recorded on the Study Drug Exposure CRF will be divided by the weight (kg) at that visit (Vital Signs CRF). If the dose (mg) is missing but the total duration of infusion is at least 50 minutes which is the lower limit of the protocol specified time (i.e. 60 min – 10 min), and IV completed is marked “Yes” then dose strength will be imputed to be equal to the planned dose strength (described below).
 - For each visit in parent study, the total dose (mg) reported will be divided by the weight used to calculate dose strength for that visit. If Current Visit is marked for Weight Used to determine dose and no corresponding weight is available from the vital sign page then the screening/baseline weight will be assigned as the weight used to calculate total dose. Dose strength will only be calculated where both the total dose and weight used are available.

Once visit/individual specific dose strengths are determined, subjects will be assigned a single average dose strength value across all visits to be used for summary statistics in the table.

- Percent of Planned Dose Strength will be determined by dividing the average dose strength per visit by the average planned dose strength per visit for each subject. Calculation of average dose strength is described above. Planned dose strength will be assigned by visit based on NEOD001 dose level. The average of planned dose strength will be the average of the individual planned dose strength calculated at each visit.

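### SAP 9.1 fills a missing dose at full planned strength, on two conditions that cannot recognise a 50% dose reduction

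*SAP*

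**What the plan says.** SAP 9.1 derives dose strength at each OLE visit as recorded mg divided by weight at that visit. If mg is missing, planned dose strength is substituted on two conditions: that "the total duration of infusion is at least 50 minutes which is the lower limit of the protocol specified time", and that the IV completed field is Yes. Planned strength is assigned by visit from the NEOD001 dose level. Visit values are averaged within subject and compared with planned strength. A dose reduction is counted each time the percent of planned dose falls below 100.

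The duration in that check depends on start and stop times, which SAP 4.3 imputes when missing, in two steps.

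- Vital signs come first. For a missing start, "start time will be imputed as the pre-dose time of vital signs at the same" visit, plus one minute. For a missing stop, "If stop time is missing for an infusion where the volume is greater than 0 mL then stop time will be imputed" from the vital signs taken just after the infusion, minus one minute.
- A fixed fallback comes second. For a missing start its condition reads "If vital sign assessment times are not available, infusion start date/time is missing, and infusion stop date/time is non-missing", and the start is then set to "stop date/time - 2 hours at the Month 1 Day 1 visit or as the stop date/time - 1 hour for all other visits". The mirror rule sets a missing stop to "start date/time + 2 hours at the Month 1 Day 1 visit or as the start date/time + 1 hour for all other visits".

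On dose, protocol 5.3 makes up each infusion to a total bag volume of 250 mL. Protocol 5.4.3 provides that drug-related AEs "may be managed by a 50% reduction in dose", for as long as the investigator chooses. Protocol 5.4.2 also halves both dose and rate when dosing continues after a Grade 3 infusion reaction.

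On duration, protocol 6.1.2 says for Month 1: "Administer NEOD001 IV using the infusion duration established during Study NEOD001-001" or over 60 (±10) minutes. It gives the same two options for later months after a well-tolerated Month 1 infusion. Protocol 5.3 and SAP 2.2.2 state the rule with no Month 1 exception.

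**The concern.** The two conditions serve as evidence that the planned dose was given. What they show is that a bag ran for long enough and was emptied. They say nothing about how much drug was in it, which is the quantity being imputed. The rule is therefore uninformative in the one situation where planned and actual dose differ by design, and its error runs one way, toward full dosing.

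The primary objective is long-term safety and tolerability. Dose strength, percent of planned dose and the number of reductions are the exposure summaries a reader would use to judge whether subjects stayed on full dose. A reduction hidden by imputation makes tolerability look slightly better than it was.

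A second weakness sits in the duration condition. Where the SAP 4.3 fallback supplies a missing time, the duration is a constant chosen by the plan, so the check tests that constant and not the infusion.

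**Working it through.** **1. The plan's own threshold.** SAP 9.1 derives it as 60 − 10 = 50 minutes. This reproduces.

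**2. Full and reduced infusions under the rule, mg missing.** Inputs: 24 mg/kg and 250 mL (protocol 5.3), 50% reduction (5.4.2, 5.4.3), imputation and counting rules (SAP 9.1).

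| | Full dose | 50% reduced dose |
|---|---|---|
| Actual strength | 24 mg/kg | 0.5 × 24 = 12 mg/kg |
| Bag volume | 250 mL | 250 mL |
| Duration | parent-established, or 60 (±10) min | the same, or longer if the rate is halved too |
| IV completed, bag emptied | Yes | Yes |
| Credited strength | 24 mg/kg | 24 mg/kg |
| Credited percent of planned | 24/24 = 100 | 24/24 = 100 (actual 12/24 = 50) |
| Counted as a reduction | No | No |

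No input to the rule differs in a way that could separate the two columns. This holds with fully recorded times.

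**3. Effect on one subject.** With m affected visits out of n and all others at full dose, the mean is overstated by 12 × m/n mg/kg and percent of planned by 50 × m/n points.

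- n = 36 (the full treatment phase), m = 1: the true mean is (35 × 24 + 12)/36 = 23.67 mg/kg, credited as 24. The difference is 12/36 = 0.33 mg/kg, or 50/36 = 1.4 points.
- n = 12 (assumed, for a subject who stops early), m = 1: 12/12 = 1.0 mg/kg, or 50/12 = 4.2 points.

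In either case m reduction events disappear from the count.

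**4. The fallback against the 50-minute check.** The fallback yields 120 minutes at Month 1 Day 1 and 60 minutes elsewhere. The margins are 120 − 50 = 70 and 60 − 50 = 10 minutes, so both pass whatever the true duration. Crossing mg missing or present, IV completed Yes or No, and duration 60 or 120 gives 8 combinations. Planned strength is imputed in 2 of them: mg missing and IV completed Yes, at either duration. Replacing 120 by 60 changes none of the 8 results.

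**5. The Month 1 value.** 120 minutes is 120/60 = 2 times the protocol default and 120 − 70 = 50 minutes above the top of its 50 to 70 minute window. SAP 9.1 summarises infusions, interruptions, strength, reductions and months of exposure, but not infusion minutes. 120 minutes also lies below the 2.5-hour (150-minute) cut-off for prolonged infusion in SAP 9.2.2 and 9.2.6. Scheduled treatment-period PK samples begin at Month 3. The value therefore reaches listings only.

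**The case against.** The case against has several good parts.

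- **Undelivered drug.** A reader might infer that the rule credits drug that was never infused. It does not: IV completed must be Yes, and protocol 5.5 records whether each dose was completely infused. An incomplete infusion is never credited, whatever its duration.
- **Cause.** A reader might also attribute the 24-versus-12 error to the imputed times. The documents do not support that. A reduced dose with recorded times passes too, so restricting the check to recorded times would not by itself remove the error. The cause is the substitution of planned strength.
- **Scope of the fallback.** Not every imputed time is sure to pass. Vital-sign times are used first, and a duration built from them can fall below 50 minutes. The fallback needs those times to be unavailable and the other infusion time to be recorded.
- **Source of the 2 hours.** SAP 9.1 also summarises parent and OLE exposure combined, and parent infusion times are not in these documents, so the Month 1 value may have been written for the parent study. SAP 4.3 does not say so. A longer parent-established duration carried into the OLE would not explain a difference confined to Month 1.
- **Dilution and cross-check.** Averaging over visits shrinks the effect on mean strength, and SAP 9.2.6 counts AEs with action Dose Reduced independently. Both are true, but the reduction count is not averaged, and the exposure and AE tables could then disagree about the same subject.

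One defence fails. Planned strength might be read as the reduced level once a subject is on it. The SAP counts a reduction when percent of planned is below 100, so under that reading a reduced dose given as prescribed would be 100% of planned and would not be counted even when mg is recorded. The count works only if planned strength stays at the full level.

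**Conclusion.** The point holds as a defect in a stated derivation rule. When mg is missing, a completed 50% infusion meeting the duration condition is recorded at twice its actual strength and drops out of the dose-reduction count. This rests on planned strength meaning the full 24 mg/kg level.

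The likely effect on average strength is small, and the documents do not say how often mg is missing or doses are reduced, so the total cannot be estimated. The reduction count is the more exposed output, since each affected visit removes a whole event. AE incidence in SAP 9.2.1 uses subject counts and exposure intervals, not mg/kg, and is untouched.

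The fallback weakness is real but narrower, and IV completed still has to be Yes. The Month 1 discrepancy is a matter of consistency. A reader might infer that it biases the exposure table, but it enters no summary and alters no imputed dose.

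**What to change.** In SAP 9.1, where dosing records or the AE action Dose Reduced show that the subject was on a reduced dose at a visit with missing mg, do not impute full planned strength. Use the recorded reduced level or leave the dose missing, and still count the reduction. State explicitly that planned strength stays at the full level for the percent-of-planned calculation.

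Also in SAP 9.1, apply the 50-minute check only to recorded start and stop times. Where a time was imputed, leave the dose missing. Both changes are needed, because neither does the work of the other.

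In SAP 4.3, reconcile the Month 1 fallback with protocol 5.3 and 6.1.2 and SAP 2.2.2, or state that it applies to parent-study infusions only.

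The cost is SAP wording and a few lines of derivation code, with a few more visits showing a missing dose. Reporting the number of visits with imputed dose strength beside the exposure table would show whether the issue mattered.
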